3.2 Study population

This study will include up to ten (10) subjects meeting all the inclusion criteria and none of the exclusion criteria, and giving their informed consent to participate in the study.

Inclusion criteria

1. Written informed consent before any study procedure is performed.
2. Subjects of both sexes aged 18 years or older.
3. Patients diagnosed with liver cancer, including HCC or liver metastases from breast, lung, pancreas and/or colorectal cancers. If biopsy is required, there will be a minimum of 2-week period after biopsy and before the ablation.
 - HCC patients must meet the United Network for Organ Sharing and Organ Procurement and Transplantation Network (UNOS-OPTN) class 5 criteria for HCC
 - Liver metastases patients must meet minimum criteria of liver biopsy and/or tissue diagnosis of primary tumor or metastatic tumor with new or growing liver tumors radiologically consistent with metastases.
4. Patients with liver cancer not candidates for surgical resection and/or not suitable for other locoregional treatments or patients who have not responded to or relapsed from conventional therapies.
5. Previous treatment with chemotherapy and/or radiotherapy is permitted provided that these treatments have been discontinued more than 2 weeks before the ablation of the targeted tumor and whenever patients have recovered from any related toxicity.
6. Previous treatment with immunotherapies is permitted provided that these therapies have been discontinued at least 4 weeks before the ablation and whenever patients have recovered from any related toxicity.
7. Previous ablation/surgery on other tumors different from those that will be targeted with the VORTX Rx® is allowed whenever a minimum of 2 weeks has elapsed since the prior procedure(s).
8. Tumor(s) to be targeted for ablation will be clearly separated from other tumors or other critical areas upon investigator's criteria.
9. Largest diameter of targeted tumor(s) ≤ 3 cm.
10. Tumor(s) that will be targeted at a depth < 10 cm from the skin surface.
11. Must have an adequate acoustic window in the abdominal space to be able to visualize targeted tumor(s) using ultrasound imaging; also, must be able to visualize targeted tumor using MRI with optional CT imaging at investigator discretion.
12. Patients who can safely undergo general anaesthesia.

13. Liver function score of Child-Pugh A or Child-Pugh B.
14. ECOG PS 0, 1 or 2 at screening.

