15. Adequate liver function (ALT and AST < 2.5 x upper limit of normal [ULN]), renal function (serum creatinine <2 ULN and/or bilirubin <2.5 UNL) and hematologic function (neutrophil count > 1.0 x 10⁹/L and platelet > 50 x 10⁹/L).
16. An INR <2 within the last 7 days prior to the ablation in patients receiving anticoagulants, and an INR <1.5 for patients not treated with anticoagulants.
17. Platelets level >50 x 10⁹/L within the last 7 days prior to the ablation

Exclusion criteria

1. Patients who decline or are unable to understand, provide or are unwilling to sign an informed consent form.
2. Pregnant or nursing (lactating) women; women of childbearing potential and sexually active that are unwilling to use adequate contraception (such as oral contraceptives, intrauterine contraceptive device or barrier method with spermicide or surgical sterilization).
3. Targeted tumor(s) not clearly separated.
4. Targeted tumor(s) >3 cm.
5. Tumor that will be targeted >10 cm from the skin surface.
6. Tumor not clearly visible with diagnostic ultrasound and MRI.
7. Liver function score of Child-Pugh C.
8. Liver volume reserve <40% as measured by CT Scan.
9. Major surgical procedure, biopsy or significant traumatic injury <2 weeks prior to the procedure or has not recovered from side effects/complications of such procedure or trauma.
10. Patient who has not recovered to grade 1 or better from any AEs (except alopecia, fatigue, nausea, vomiting) related to previous anti neoplastic therapies.
11. BMI >30.
12. Parkinson's disease.
13. History of bleeding disorders (e.g. von Willebrand disease) or patients suspected to have a bleeding disorder.
14. Not able to temporarily discontinue warfarin, clopidogrel or any other long-acting anticoagulants at least two weeks before the procedure.
15. Initiation of any anticancer treatment during the screening period.
16. Life expectancy to be less than 6 months.
17. ASA score ≥ 4.

18. Unable or unwilling to complete all required screening and/or follow-up assessments.
19. Patients under ongoing treatment with an investigational medication or medical device that conflicts with the study device.
20. Patients for whom the investigator considers that the ablation is not in the patient's best interest.
21. Patients with active alcohol or drug addiction or any other condition that, in the investigator's opinion, would interfere with their ability to comply with the study requirements.

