4 METHODOLOGY

Quantitative variables will be described with measures of central tendency and dispersion: mean, median, SD (standard deviation), Q1 (first quartile) and Q3 (third quartile), minimum and maximum).

Qualitative variables will be described using absolute and relative frequencies (N, %). Two percentage columns will be presented, total percentage (total %) and valid percentage (valid %), that is, the percentage over the sum of valid responses plus missing values and the percentage over the total of valid responses. When there will be not missing values both of them will be equal, and then only one will be shown.

In the analysis of parameters evolution (ablation zone, liver function parameters, immunological parameters, quality of life scores, VAS scale score), among visits, general linear models of repeated measures will be used. With this methodology, it is necessary that the values of the variable must be available at all visits for all patients.

Where an inferential analysis is required, parametric tests shall be used for continuous variables (T-test) that follow a normal distribution. For variables that do not follow a normal (or non parametric) distribution, Mann Whitney (for unpaired data) or Wilcoxon (for paired data) hypothesis tests shall be used.

These tests will be used in all bilateral cases and with a level of significance of 0.05. In cases where a p-value less than 0.05 appears, it refers to the existence of statistical significance.

Due to the number of evaluable patient ablations available, any result from an applied statistical test must be interpreted with caution.

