15.2 Secondary objectives

1. **Assessment of the safety profile of the VORTX Rx®.**

This objective is given the answer with the analyses proposed in sections 6.7.2, 6.7.3, 6.7.4, 6.7.5, 6.8, 8.2, 8.3, 8.4, 9.2, 9.3, 9.4, 9.5, 10.2, 10.3, 10.4, 10.5, 11.2, 11.3, 11.4, 11.5 and 12 of this document.

2. **Assessment of local tumor progression by MRI at 1 week, 1 month and 2 months, post-procedure.**

The following analyses will be carried out to respond to this objective:

The number of patients who have indicated local tumor progression **in at least one visit** (1 week, 1 month, 2 months) for each tumor ablated in ablation 1, ablation 2, and ablation 3 will be provided.

3. **Assessment of the involution of the ablation zone 1 week, 1 month and 2 months post-procedure.**

The following analyses will be carried out separately for each tumor (tumor 1, tumor 2, tumor 3....) to respond to this objective:

- Ablation zone volume at 24 hours post-ablation, 1-week, 1 month and 2 months post-ablation will be compared among visit using a general linear model of repeated measures.

In addition:

- Ablation zone volume at 24 hours post ablation vs ablation zone volume at 1 week will be compared using Paired T-Test or Wilcoxon depending on variable distribution.
- Ablation zone volume at 24 hours post ablation vs ablation zone volume at 1 month will be compared using Paired T-Test or Wilcoxon depending on variable distribution.
- Ablation zone volume at 24 hours post ablation vs ablation zone volume at 2 months will be compared using Paired T-Test or Wilcoxon depending on variable distribution.

4. **Assessment of liver panel.**

The following analyses will be carried out separately for each ablation (ablation 1, ablation 2, ablation 3) to respond to this objective:

- AST at Screening and at 24 hours post-procedure and the follow-up visits performed at 1 week, and 1 and 2 months post-procedure will be compared among visit using a general linear model of repeated measures.
- ALT at Screening and at 24 hours post-procedure and the follow-up visits performed at 1 week, and 1 and 2 months post-procedure will be compared among visit using a general linear model of repeated measures.
- GGT at Screening and at 24 hours post-procedure and the follow-up visits performed at 1 week, and 1 and 2 months post-procedure will be compared among visit using a general linear model of repeated measures.

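### The liver-panel objective is answered only by a test of visit means, which cannot respond to a rise confined to one patient; a per-patient count and listing should be added

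*SAP*

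**What the plan says.** Section 15.2 item 4 of the SAP covers eight parameters: AST, ALT, GGT, alkaline phosphatase, total bilirubin, albumin, PT and INR. Each "will be compared among visit using a general linear model of repeated measures". For ALT the values compared are "ALT at Screening and at 24 hours post-procedure and the follow-up visits performed at 1 week, and 1 and 2 months post-procedure", which makes five time points. The model is fitted once per ablation: "The following analyses will be carried out separately for each ablation (ablation 1, ablation 2, ablation 3) to respond to this objective". Item 4 names nothing else. It has no patient count, worst value, shift from baseline or listing, and no cross-reference to other tables.

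Three other parts of the SAP bear on this:

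- **Sample size (section 3.2).** "This study will include up to ten (10) subjects".
- **Test rules (section 4).** On the level: "These tests will be used in all bilateral cases and with a level of significance of 0.05". On reading the result: "In cases where a p-value less than 0.05 appears, it refers to the existence of statistical significance". For the repeated-measures model, "it is necessary that the values of the variable must be available at all visits for all patients". No sphericity correction is named. The section closes by asking that any test result be read cautiously, because few ablations will be evaluable.
- **Inclusion criterion 15 (section 3.2).** "Adequate liver function (ALT and AST < 2.5 x upper limit of normal [ULN" sets the only ALT and AST limit in the SAP. It applies at entry.

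**The concern.** A repeated-measures test of visit means asks whether the group average moves over time. For a liver panel after ablation in at most ten patients, a reader will also want to know whether any individual had a marked rise, how many did, and whether their values returned to where they began. A large value in one patient raises the visit mean and the error variance together, so the test gains nothing from it.

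If the only stated answer to objective 4 is a p-value of this kind, the report may leave the individual question open under the objective where it is most naturally asked. Other items in section 15.2 do count patients: item 2 counts those with local progression at any visit, and item 7 counts those given drugs for post-procedure pain.

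**Working it through.** The SAP gives no power or F figure for this objective, so there is none to reproduce.

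**Inputs.** From the SAP: n = 10 patients (the maximum), v = 5 visits, two-sided level 0.05. Not in the SAP, and therefore assumed: the size of the rise, the visit-to-visit noise and the number of patients affected.

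**Algebra.** Let m of n patients share the same change over visits, with sum of squares S about the patient's own mean, and let the others be flat.

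- SS_visit = n × (m/n)² × S = m²S/n, on v − 1 degrees of freedom.
- SS_error = mS − m²S/n = mS(1 − m/n), on (n − 1)(v − 1) degrees of freedom.
- F = [m²S/n] / [mS(1 − m/n)/(n − 1)] = m(n − 1)/(n − m).

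S cancels, so neither the size nor the timing of the rise matters. For m = 1, F = (n − 1)/(n − 1) = 1 at any n. With n = 10 and v = 5 the uncorrected critical value of F(4, 36) is 2.63. The lower-bound column refers F to F(1, 9). It equals the Greenhouse-Geisser result when all the change follows one time pattern, as it does here.

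| Patients with the same rise | F | Uncorrected p, F(4, 36) | Lower-bound p, F(1, 9) |
|---|---|---|---|
| 1 of 10 | 9/9 = 1.00 | 0.42 | 0.34 |
| 2 of 10 | 18/8 = 2.25 | 0.083 | 0.17 |
| 3 of 10 | 27/7 = 3.86 | 0.010 | 0.081 |
| 4 of 10 | 36/6 = 6.00 | 0.0008 | 0.037 |

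**With visit noise.** Simulation of 20,000 trials per setting used n = 10, five visits, normal noise and no common change. One patient rises at 24 hours by a multiple of the within-patient SD.

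| Rise in one patient | Median F (5th to 95th percentile) | Uncorrected rejection |
|---|---|---|
| 0 SD | 0.85 (0.18 to 2.63) | 4.9% |
| 5 SD | 0.88 (0.20 to 2.52) | 4.3% |
| 10 SD | 0.94 (0.28 to 2.13) | 1.6% |
| 20 SD | 0.97 (0.50 to 1.63) | 0.0% |
| 50 SD | 1.00 (0.77 to 1.26) | 0.0% |

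Rejection never rises above the chance level, and falls as the isolated rise grows. The multivariate (Hotelling) form of the test stays at about 4 to 5% throughout.

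**Masking.** If all ten patients rise by 2 SD at 24 hours, median F is 8.9 and uncorrected rejection 99.5%. Adding a further 20 SD in one patient leaves rejection at 93.3%; adding 50 SD cuts median F to 1.9 and rejection to 0.2%. Masking therefore needs a very large value. With a common rise of 1 SD, a further 5 SD in one patient in fact raised rejection from 54.4% to 72.4%.

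**What the other tables would show.** Take ALT with mean 30, between-patient SD 8 and within-patient SD 6, and one patient peaking near 1000 at 24 hours and then declining (all assumed). Median F is 1.00 and rejection 0%. The 24-hour laboratory table would show a maximum of about 1000, a mean of about 127, an SD of about 307 and a median of about 31.

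**The case against.** The strongest reply is that the SAP does not leave an isolated injury unseen. Sections 8.4, 9.5, 10.5 and 11.5 give mean, SD, quartiles, minimum and maximum of every liver test at each visit, and the illustration above would stand out in them. Child-Pugh category, built on fixed cut-offs for bilirubin, albumin and INR together with ascites and encephalopathy, is tabulated at every post-ablation visit. Section 12 counts patients by adverse event grade and lists serious events by patient. Safety is objective 1, and section 15.2 answers it from the laboratory tables and section 12. Objective 4 is a separate description of how the panel evolves, for which comparing visit means is legitimate. Section 4 also urges caution with every test. Finally, the entry limit for ALT and AST is an eligibility rule, and nothing obliges the SAP to reuse it.

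Most of this stands. A reader might infer that isolated liver injury would be reported as no change, or that the safety question itself rests on this test; the sections just listed do not support either reading. A reader might also infer that F is always 1, or that ten patients is the cause. It is exactly 1 only when the others are flat, and it is so at any n. Nor is the test blind to several affected patients: without a correction, three of ten already reach p = 0.010.

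What the reply does not supply is the patient-level answer:

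- A per-visit maximum does not say how many patients were abnormal, and is not tied to the patient's own baseline or ULN.
- Child-Pugh does not use ALT, AST, GGT or alkaline phosphatase, and its sections are cited under neither objective 1 nor objective 4.
- Adverse event tables include a laboratory change only if it was recorded as an event.

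**Conclusion.** The point holds as a weakness in how objective 4 is answered. The one analysis named under item 4 cannot be made significant, beyond chance, by a rise in a single patient, and two of ten equally affected patients also fall short of 0.05.

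The exact F values assume that unaffected patients are flat and that affected patients share one profile. The simulated rates assume normal noise and complete data. That liver effects would fall on one or a few patients is a premise of this check and is not stated in the SAP. The complete-data rule adds to the problem: in the usual fitting of such a model, an affected patient who misses a visit drops out of it altogether.

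Because other tables can reveal an isolated case, this is a cheap improvement to the reporting and not an error that undermines the study's safety assessment.

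**What to change.** In section 15.2 item 4, make a per-patient summary the main answer:

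- Number and percentage of patients, at each visit and at any post-ablation visit, with ALT or AST at or above 2.5 x ULN. This is a reporting cut-off only. It is convenient because inclusion criterion 15 puts every eligible patient below it at entry.
- For GGT, alkaline phosphatase, bilirubin, albumin, PT and INR, the number of patients newly outside the laboratory's normal range, as a shift from Screening.
- A listing of the full series of each such patient, including those with a missed visit.
- A cross-reference to the laboratory tables (6.8, 8.4, 9.5, 10.5, 11.5) and the Child-Pugh tables (6.9, 8.5, 9.6, 10.6, 11.6).
- The repeated-measures comparison kept, labelled supportive.

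The cost is some SAP wording, one table and one listing from values already collected. The ULN for ALT, AST and bilirubin is already needed to apply inclusion criterion 15. The normal ranges for the other parameters should be confirmed as available from each centre's laboratory.
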